## **Skin Toxicity**

Management guidelines for subjects experiencing skin toxicity are as follows:

- Grade 1 or 2 skin reactions
  - Symptomatic treatment with low-dose topical corticosteroids (betamethasone 0.1% or hydrocortisone 1%) or antihistamines (diphenhydramine).
  - Persistent Grade 1 or 2 rash should be managed with higher dose topical corticosteroids and/or oral prednisone (1 to 2 mg/kg/day) if there is no improvements with topical therapies or the rash is accompanied by other dermal toxicities such as pruritus.
- Grade 3 skin reactions Withhold MGD013.
  - Initiate oral corticosteroids (oral prednisone 1 to 2 mg/kg/day).
  - MGD013 may be restarted at the next scheduled dosing if symptoms resolve to ≤ Grade 2 within 14 days.
  - A Grade 3 skin toxicity that does not resolve to ≤ Grade 2 within 14 days after oral corticosteroids requires permanent discontinuation of MGD013.
- Grade 4 skin reactions Discontinue MGD013.
  - Initiate oral corticosteroids (oral prednisone 1 to 2 mg/kg/day).
  - Consideration should be given to start IV corticosteroids (methylprednisolone 1-2 mg/kg/day) for Grade 4 skin toxicities; methylprednisolone should be tapered over 30 days if resolved to < Grade 2.

#### **Nephritis**

Management guidelines for subjects experiencing nephritis are as follows:

- Grade 1 nephritis No specific therapy required; close monitoring of renal function.
- Grade 2 nephritis Withhold MGD013.
  - Consider nephrology consultation and renal biopsy to confirm interstitial nephritis.
  - Initiate corticosteroids: 1 to 2 mg/kg/day of oral prednisone or equivalent divided twice daily. Taper over 4 weeks as clinically indicated.
  - Resume MGD013 at next scheduled dose if:
    - Nephritis resolves to ≤ Grade 1 within 14 days with or without treatment

- Grade 3 and 4 nephritis Permanently discontinue MGD013.
  - Consider hospitalization, nephrology consultation, and renal biopsy to confirm interstitial nephritis.
  - Initiate corticosteroids: 2 to 4 mg/kg/day of oral or IV methylprednisolone or equivalent divided twice daily. Taper over 4 weeks as clinically indicated.

### **Immune-Mediated Hypophysitis**

Management guidelines for subjects experiencing hypophysitis are as follows:

- Grade 1 hypophysitis No specific therapy required.
- Grade ≥ 2 hypophysitis Withhold MGD013.
  - Consult endocrinologist.
  - Consider hospitalization.
  - Consider a short course of high dose IV corticosteroids: e.g., methylprednisolone 2-4 mg/kg/day IV (or equivalent) divided twice daily.
  - Initiate hormonal replacement therapy as indicated.
  - MGD013 may be resumed as allowed by protocol when:
    - Endocrinopathy is controlled with appropriate replacement therapy.
    - Corticosteroids reduced to  $\leq 10$  mg/day prednisone or equivalent.
  - Brain MRI recommended.

### **Thyroid Toxicity**

Thyroid disorders may occur at any time during treatment with MGD013. Monitor subjects for changes in thyroid function and for clinical signs and symptoms of thyroid disorders per protocol and as indicated by clinical evaluation. Isolated hypothyroidism may generally be managed with replacement therapy without treatment interruption or corticosteroids, and treatment guidelines for hyperthyroidism are recommended below:

- Grade 1 hyperthyroidism No specific therapy required.
- Grade 2 hyperthyroidism Withhold MGD013.
  - Consider initiating oral corticosteroids.
  - A short course of corticosteroids such as methylprednisolone 1 to 2 mg/kg/day IV (or equivalent) divided twice daily.
  - MGD013 will be resumed if it is reduced to ≤ 10 mg/day prednisone or equivalent and stable on hormone replacement therapy (if necessary).
- Grade 3 or 4 hyperthyroidism Withhold MGD013.
  - Consider hospitalization and consulting endocrinologist.
  - IV corticosteroids such as methylprednisolone 2 to 4 mg/kg/day IV (or equivalent) divided twice daily.
  - Initiate hormonal replacement therapy as indicated.
  - Consider restarting MGD013 when complete resolution or disease stable on hormone replacement therapy within 14 days and it is reduced to ≤ 10

mg/day prednisone or equivalent.

### 8.4.2 Brivanib Alaninate-related Adverse Reactions

## **Management of Hypertension**

In case of hypertension during treatment with angiogenesis inhibitors, investigators should take measures according to the best practices of drugs. The following treatment guideline may be adopted according to experience of previous antiangiogenic therapy. Consider cardiologist consultation to recommend the optimal dose and combination regimen in case of uncontrollable hypertension.

- Persistent mild hypertension (systolic pressure: 140 149 and / or diastolic pressure: 90-99 mmHg)
- Treatment:
  - Initiate or add one antihypertensive agent at a stating dose (recommendation: enalapril or hydrochlorothiazide). Increase the dose gradually until blood pressure (BP) is under control.
  - No dose adjustment of study drugs
- Persistent moderate hypertension (systolic pressure: 150 179 and / or diastolic pressure 100 - 109 mmHg)
- Treatment:
  - Initiate or add one long-acting antihypertensive agent, which gradually increases to the maximum until improvement to mild hypertension.
  - Add the second drug if BP is partially controlled or not controlled, increase the dose gradually to the maximum until BP is under control.
  - Add the third antihypertensive agent if BP is not controlled or partially controlled within the moderate range, increase the dose gradually to the maximum until BP is under control.
  - When it is controlled to mild hypertension, it can be de-escalated to the next level according to the dose of brivanib alaninate.
- Persistent severe hypertension (systolic pressure >180 and / or diastolic pressure: >110 mmHg)
- Treatment with symptoms:
  - Discontinue the investigational drug
  - Monitor BP closely. Beware of hypotension while discontinuing the investigational drug
  - Consider hospitalization for close monitoring and IV treatment
  - Treat as a hypertensive crisis.
- Treatment if there is no symptom:
  - Suspend the investigational drug and monitor BP closely
  - Initiate or add two antihypertensive agents, which gradually increase to the maximum until BP is under control.
  - If BP is not controlled, but there is no symptom, add one drug that increases

- gradually to the maximum until BP is controlled.
- When it is controlled to mild hypertension, resume the investigational drug that is considered to be de-escalated to the next level according to the dose taken by the subject
- Discontinue the investigational drug if it is still not controlled with three antihypertensive drugs at the maximum dose
- Hypertensive crisis (diastolic pressure > 120 mmHg; systolic pressure > 180 mmHg or CNS, cardiovascular and kidney involvement)
- Treatment:
  - Discontinue the investigational drug
  - Immediate treatment

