## 4.3 Discontinuation of Subjects from Treatment

### 4.3.1 End of Treatment

Subjects may discontinue treatment at any time during the study. End of Treatment Visit (EOT) should be performed within 7 days of decision date to discontinue treatment.

Study drug shall be permanently discontinued in any of the following cases:

- Adverse Event
  - Occurrence of any CTCAE (V5.0) grade 3 or 4 treatment-related adverse event, which fails to recover to CTCAE Grade 1 or below within 4 weeks (28 days) (unless the investigator believes that the subject may continue to benefit from treatment and the continuation requires the permission from sponsor's medical monitor);
  - CTCAE Grade 3 or 4 treatment-related adverse event recurs in combination treatment group despite dose reduction of brivanib alaninate;
  - Myocardial ischemia and/or infarction;
  - Evidence for abnormal cardiac valve function ≥ CTCAE Grade 2;
  - LVEF decrease by > 10% from baseline-ECHO and LVEF < 45%;
  - QTc > 500 milliseconds on 3 consecutive ECGs performed during the same visit and in the absence of possible causes other than study therapy;

- Torsade de pointes or sustained ventricular tachycardia;
- Hemorrhage ≥ CTCAE Grade 3;
- Gastrointestinal perforation;
- Arterial thromboembolic event;
- Venous thromboembolic events of CTCAE Grade 3 or 4;
- Hypertensive crisis;
- Immune-related adverse events of grade 4.
- Disease progression according to irRECIST criteria
- Risk to the subject as judged by the investigator and/or sponsor
- Critical violation to the protocol as judged by the investigator and/or sponsor
- Subject's decision
- Pregnancy
- Death
- Completion of protocol-defined therapy (MGD013 monotherapy)

If the reason for treatment discontinuation is not disease progression, death, withdrawal of informed consent or loss to follow-up, radiologic tumor assessments will still be performed at protocol-specified intervals until disease progression by irRECIST or the starting of subsequent antitumor therapy (Phase II).

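### Two pairs of dosing rules contradict each other as written: recovery of raised transaminases to baseline, and a first related Grade 3 hyponatremia

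*Combined protocol and SAP*

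**What the plan says.** **Transaminases.** Section 4.1 admits subjects with ALT and AST up to 5 × ULN (subjects with HCV infection are held to Grade 1), and Section 3.1.3 sets separate DLT criteria for a Grade 2 baseline of 3 to 5 × ULN. In Section 8.4.1.2 (Hepatotoxicity), for a rise above 5 and up to 8 × ULN:
- Stop rule: discontinue MGD013 if Grade 2 is not reached by day 7 and Grade 1 by day 14.
- Resume rule: restart if Grade 2 or lower by day 7, Grade 1 *or baseline* by day 14, and steroids are at 10 mg/day prednisone equivalent or less.

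Section 8.4.3, for combination subjects, allows resumption at Grade 1 or at a higher baseline grade. Its next sentence stops both drugs for good if Grade 1 is not reached in 28 days. The 28-day bullet in Section 4.3.1 has no baseline clause either, but lets treatment continue if the investigator sees benefit and the medical monitor agrees.

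**Hyponatremia.** Table 5 continues drug, with medical treatment, at a first Grade 3 event. Section 8.4.3 halts both drugs for any related Grade 3 or 4 event. It exempts drug-controlled hyponatremia and hypertension, but only from the stop on recurrence after dose reduction. The matching bullet in Section 4.3.1 has no exemption: "CTCAE Grade 3 or 4 treatment-related adverse event recurs in combination treatment group despite dose reduction of brivanib alaninate".

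**Blood pressure (8.4.2).** The severe band is "Persistent severe hypertension (systolic pressure >180 and / or diastolic pressure: >110 mmHg". Without symptoms, the action is "Suspend the investigational drug and monitor BP closely" and later "When it is controlled to mild hypertension, resume the investigational drug". The next band is "Hypertensive crisis (diastolic pressure > 120 mmHg; systolic pressure > 180 mmHg or CNS, cardiovascular and kidney involvement", with discontinuation. Section 4.3.1 lists "Hypertensive crisis" under "Study drug shall be permanently discontinued in any of the following cases".

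**Grade 4 endocrine events.** The same list in 4.3.1 holds "Immune-related adverse events of grade 4", and 8.4.3 stops MGD013 permanently for any drug-related Grade 4 event. In 8.4.1.2, a restart may be considered after Grade 3 or 4 hyperthyroidism, and MGD013 may be resumed, as far as the protocol allows, after hypophysitis of Grade 2 or higher.

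**The concern.** For transaminases and hyponatremia, two instructions call for opposite actions in the same subject. As written, the transaminase stop rule ends treatment in an eligible subject who has fully returned to the level at entry. For blood pressure and Grade 4 endocrine events, a stricter and a more lenient text cover the same patient.

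Safety is a primary objective in every phase, and Section 9.3.1 summarises adverse events leading to discontinuation. With about 25 sites, like events could be handled differently, and that table would then partly reflect which sentence a site followed.

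**Working it through.** The plan states no figure to reproduce. The check is whether one subject can meet both triggers. Grades follow the protocol's own multiples: 3 to 5 × ULN is Grade 2, and above 5 to 8 × ULN falls under Grade 3 (Section 8.4.1.2).

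**1. Transaminases.** Take a treatment-related rise: baseline 4 × ULN, peak 6, day 7 = 4, day 14 = 4, steroids tapered to 10 mg/day or less.

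| Rule | Test | Result |
|---|---|---|
| 8.4.1.2 resume | Grade 2 or lower by day 7; Grade 1 or baseline by day 14; steroids low | all met: resume |
| 8.4.1.2 stop | Grade 1 by day 14 | not met: discontinue |
| 8.4.3, day 28 still 4 (combination) | Grade 1 by day 28 | not met: permanent stop |
| 4.3.1, day 28 still 4 | Grade 1 by day 28 | not met: permanent stop unless waived |

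With baseline at Grade 1 or lower, returning to baseline also meets the Grade 1 test, so the conflict is confined to subjects entering above Grade 1.

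**2. Hyponatremia.** First related Grade 3 event in a combination subject: Table 5 says continue; 8.4.3 says halt both drugs. Because 8.4.3 goes on to describe resumption, its halt is an interruption. The conflict is continue versus interrupt. The exemption does not reach a first event. On recurrence after dose reduction, 8.4.3 exempts a drug-controlled event and 4.3.1 does not.

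**3. Blood pressure, persistent and without symptoms or organ involvement.**

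| Reading | Severe band | Crisis, limits joined by *or* | Crisis, limits joined by *and* |
|---|---|---|---|
| 185/125 | yes | yes | yes |
| 185/105 | yes | yes | no |
| 175/115 | yes | no | no |

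The first reading is in both bands however the semicolon is read. For the second, the missing joining word decides the action.

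**4. Illustrative counts.** Section 9.2 enrols 34 + 45 = 79 per treatment in Part 1; 2 × 79 = 158 agrees with the synopsis. Part 2 has 120. Earlier rates (Sections 1.1.3.2 and 1.1.4.2.3) are assumed to carry over.
- Grade 3/4 ALT increase with brivanib, 9%: 0.09 × 79 = 7.1; in Part 2, if the combination is chosen, 0.09 × 120 = 10.8. AST, at 7%, gives 0.07 × 79 = 5.5 and may overlap. Only subjects entering at 3 to 5 × ULN count, and their share is not given. The same 8.4.1.2 rules also apply to monotherapy.
- Hyponatremia of any grade, about one third: 79/3 = 26.3; 120/3 = 40. Grade 4 was 4%. No Grade 3 rate is given.
- Grade 3/4 hypertension, 5%: 0.05 × 79 = 3.95; 0.05 × 120 = 6. Asymptomatic crisis-range readings are a part of this.
- Related Grade 4 events with MGD013: 0 of 36. Exact two-sided 95% upper limit 1 − 0.025^(1/36) = 9.7%, for all such events together.

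**The case against.** The best reply is that the intended action can mostly be seen. Table 5 is the event-specific rule, and 8.4.3 refers brivanib-related restart decisions and the two exempted events to 8.4.2. The baseline allowance appears in the resume rule directly under the stop rule and again in 8.4.3, so many readers would carry it over. Section 8.4.1.2 also calls its content general guidelines. This lowers the likely harm. It does not remove the contradiction: no text says that the specific rule prevails, and in the transaminase case both rules stand in the same section.

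The reply succeeds for blood pressure and Grade 4 endocrine events. A reader might infer that these are further contradictions of equal weight. The documents do not support that: 4.3.1 is mandatory, the hypertension steps are offered as an option, a hyperthyroidism restart is only to be considered, and the hypophysitis text defers to the protocol. Taking the stricter action satisfies both texts. Leniency for controlled endocrine events may even be intended, since Section 3.1.3 excludes controlled Grade 3 endocrinopathy from DLT.

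A reader might also infer that anyone spared at day 14 must be stopped at day 28. The waiver in 4.3.1 prevents so flat a statement, although 8.4.3 repeats the 28-day stop without one.

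**Conclusion.** The concern holds for two contradictions: the transaminase stop and resume rules, with the related 28-day sentences, and the first related Grade 3 hyponatremia in combination subjects. The blood pressure and Grade 4 endocrine overlaps are secondary clarifications.

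The number affected is unknown and probably small. The counts above are illustrative. Reading them as upper bounds would be wrong: they leave out Phase I combination subjects, and the brivanib rates do not describe the monotherapy cohort.

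Two more stronger readings are not supported. The Grade 2 transaminase rule lacks a baseline allowance, but nothing there contradicts it. The bilirubin rules differ in outcome only if a subject enters above Grade 1; entry allows up to 2.5 × ULN, but the documents do not give the boundary between Grades 1 and 2, so that is an assumption. Nor do the documents show an effect on the efficacy result: they do not class following one of two conflicting dosing sentences as a serious deviation that would remove a subject from the PPS. No effect on sample size, alpha, power or ORR is claimed. The text should be corrected because, read literally, it withdraws treatment from eligible subjects who have recovered to baseline.

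**What to change.** 1. **Transaminases.** Add *or baseline* to the 14-day stop rule for rises above 5 and up to 8 × ULN in 8.4.1.2, and to the 28-day rules in 8.4.3 and 4.3.1. Carry it to the Grade 2 transaminase and bilirubin stop rules for consistency only.
2. **Hyponatremia.** Extend the existing exemption in 8.4.3 to its interruption sentence and to the recurrence bullet in 4.3.1. Alternatively, change Table 5 to interrupt at the first Grade 3 event. Either is workable if all three places agree.
3. **Blood pressure.** Cap asymptomatic severe hypertension below the crisis limits and without organ involvement, and write *and* or *or* between the crisis limits.
4. **Grade 4 endocrine events.** Make the hyperthyroidism and hypophysitis restart text agree with the permanent stop in 4.3.1 and 8.4.3, by limiting it to lower grades or by stating an endocrine exception.
5. **Precedence.** Add one sentence saying which section governs if 4.3.1 and 8.4 differ.

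The cost is a protocol text amendment with ethics approval before use (Section 10.6). It needs no new data, visits or subjects.

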#### Management of Hyponatremia

In the study of brivanib alaninate, about 1/3 subjects experienced > Grade 1 hyponatremia. In addition, hyponatremia is a common complication of hepatic cirrhosis and ascites. Therefore, blood biochemistry and renal and liver function should be monitored periodically in advanced HCC subjects receiving brivanib alaninate. It is recommended to adopt medical interventions in case of CTCAE Grade 1 hyponatremia.

Table 5: Management of Hyponatremia Related to Brivanib Alaninate

Electrolytes		
Hyponatremia CTCAE Grade 3: <130-120 mmol/L	The first occurrence	Continue the investigational drug and begin medical intervention until blood sodium $\geq 130 \text{ mmol/L}$
	Last for ≥ 7 days or occur for the second	Suspend the investigational drug and begin medical intervention
	time	Resume the investigational drug if blood sodium $\geq 130$ mmol/L, consider to reduce the dose to level -1
	The third occurrence	Discontinue the investigational drug or discuss with medical monitors
Hyponatremia CTCAE Grade 4:	The first occurrence	Suspend the investigational drug and begin medical intervention
<120 mmol/L		Resume the investigational drug if blood sodium $\geq 130$ mmol/L, consider to reduce the dose to level -1
	The second occurrence	Discontinue the investigational drug or discuss with medical monitors

### 8.4.3 Toxicity and Management of Combination Toxicity

No new AEs other than toxicity related to single drug are anticipated for the combination of MGD013 and brivanib alaninate for they have different mechanism of action. However, some adverse reactions, e.g., thyrotoxicity and hepatotoxicity, may overlap. The combination medication group should be closely monitored for AEs. Both investigational drugs should be discontinued in case of any adverse events with CTCAE Grade 3 to 4 and causally related to study treatment. Before the study drug is resumed, the appropriate medical intervention should be applied until the AE is resolved to CTCAE Grade ≤1 (or baseline level if the event severity is higher than CTCAE Grade 1 at baseline). If the AE fails to be resolved to CTCAE Grade ≤1 within 28 days upon event onset, both study drugs should be

permanently discontinued and the subject should be withdrawn from the study.

When study treatment is to be resumed, if the investigator considers that the AE is related to brivanib alaninate, the treatment can be restarted at the original dose or dose reduced to next lower level as pre-defined, depending on the dose originally administered and event severity (See 8.4.2). In Phase I study, dose reduction is not allowed during the DLT observation period and permitted at most once for the remaining period. If treatment-related AE of CTCAE Grade 3-4 occurs again after dose reduction, the study treatment will be discontinued (except hyponatremia and hypertension that can be controlled by drugs, see 8.4.2). Once reduced, the dose should be maintained at lower level and dose escalation is never allowed.

Given the mechanism of action of MGD013, it is anticipated that activation of cellular immune system can be manifested as immune-related AEs (irAEs). The fundamental principles of managing irAEs are suspension of the immune checkpoint inhibitor (ICI), a course of corticosteroids and routine supportive measures are given based upon the severity of Grade 1 - 2 irAEs, and restart the treatment without adjusting the dose after adverse events are resolved; discontinue MGD013 in case of drug-related Grade 3 adverse events and restart the drug after resolving to  $\leq$  Grade 1 or baseline; permanently discontinue MGD013 and terminate the study in case of any drug-related Grade 4 adverse events. Guidelines for irAE management are available through the American Society of Clinical Oncology and National Comprehensive Cancer Network

(https://www.nccn.org/professionals/physician\_gls/pdf/immunotherapy.pdf) or the European Society of Medical Oncology (https://www.esmo.org/Guidelines/Supportive-and-Palliative-Care/Management-of-Toxicities-from-Immunotherapy). In the study, clinical management of MGD013-related adverse events is shown in 8.4.1.

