### 4.3.2 End of Study

Patients who are no longer on treatment but are still followed on the study can be terminated from the study for the following reasons:

- Death
- Lost to follow up
- Withdrawn of consent
- The study is terminated

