# 6.4 Post-Treatment Assessments (Subjects in phase II are not required to have visits in the study site)

- Subjects will receive survival follow-up and subsequent treatment follow-up to collect
  - the information (including commencement date of subsequent first anti-tumor treatment) of first anti-tumor treatment (including chemotherapy) after the end of study treatment every 60 days (± 7 days)
  - Subjects will receive survival follow-up after discontinuation of study treatment every 60 days (± 7 days) to collect the information of new malignant tumors
- Monitoring of SAEs and irAEs: study treatment-related SAEs or irAEs ≥ grade 3 occurring within 30 days after the last dose should be recorded and evaluated.
- Tumor imaging assessments and serum AFP: If the subject is withdrawn from the treatment for reasons other than radiographic progression, the subject will still need to undergo imaging scans and AFP testing every 8 weeks (± 1 week) after discontinuation of study treatment until tumor progression is confirmed or subsequent antineoplastic therapy is initiated

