## 8.3.2 Follow-up of Adverse Events

Investigators must follow up all adverse events until their disappearance or recovery to baseline, up to disease stable in case of permanent injury; if an adverse event is not recovered at the last visit of the study, investigators must continue to follow up the adverse event until disappearance or recovery to baseline level, or clinical stability. Subsequent follow-up may not be recorded in the eCRF, but the sponsor has the right to ask investigators to provide more information where necessary.

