## 8.3.10 Pregnancy

Effective contraception is required for both male and female subjects of childbearing potential during the study and within 120 days after discontinuation of investigational drug treatment. Once pregnancy is found to be pregnant following initiation of study treatment, the investigational drug will be permanently discontinued and the female subject will be withdrawn from the trial. If a female subject or a male subject's partner becomes pregnant during the study or within 4 months after the last dose of investigational drug adminstration, the investigator should be notified immediately. The pregnancy must be recorded on "Pregnancy Reporting Form" and reported by the investigator to the Sponsor via email within 24 hours of becoming aware of the event. At the same time, the pregnancy also must be recorded on eCRF. All pregnancies must be followed until the end of pregnancy, and the sponsor should be informed of the pregnancy outcome information. If the outcome of the pregnancy meets SAE criteria (e.g., spontaneous abortion/miscarriage or therapeutic abortion with any detected congenital anomaly, stillbirth, neonatal death, or birth defect), it will be reported as SAE. The investigator should send the completed "SAE Reporting Form" to the Sponsor via email within 24 hours of becoming aware of the event. All pregnancies during the trial or within 120 days after the last dose of investigational drug should be handled in accordance to the procedure described in this section.

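### Section 8.4.3 removes subjects with unresolved toxicity from the study, where Sections 4.3.1, 4.3.2, 6.4 and Table 1 footnote 6 only take them off treatment; followed literally, it risks informative censoring

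*Combined protocol and SAP*

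**What the plan says.** Section 8.4.3, on combination toxicity, deals with treatment-related Grade 3-4 events. When such an event has not come down to Grade 1 or lower 28 days after it began, the two drugs are to be "permanently discontinued and the subject should be withdrawn from the study". Its paragraph on immune-related events adds: "permanently discontinue MGD013 and terminate the study in case of any drug-related Grade 4 adverse events".

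Other sections treat the end of treatment and the end of study as separate things:

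- **Section 4.3.1 (End of Treatment)** lists a related Grade 3 or 4 event not recovered in 28 days as a reason to stop study drug permanently. It allows an exception with the medical monitor's permission, and it keeps Phase II imaging going when the reason for stopping is not progression, death, withdrawn consent or loss to follow-up.
- **Section 4.3.2 (End of Study)** opens: "Patients who are no longer on treatment but are still followed on the study can be terminated from the study for the following reasons". It names four: death, loss to follow-up, withdrawn consent and termination of the study.
- **Section 6.4** says: "If the subject is withdrawn from the treatment for reasons other than radiographic progression, the subject will still need to undergo imaging scans", every 8 weeks, and plans survival contact every 60 days.
- **Table 1, footnote 6** says that subjects who leave the study because of drug toxicity still have tumour assessments every 8 weeks during survival follow-up.
- **Section 8.3.2** says of events unrecovered at the last study visit: "investigators must continue to follow up the adverse event until disappearance or recovery to baseline level, or clinical stability".

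Section 8.3.10 has similar wording for pregnancy: "the investigational drug will be permanently discontinued and the female subject will be withdrawn from the trial". Section 4.3.1 lists pregnancy as a reason to stop drug, and 4.3.2 does not list it as a reason to leave the study.

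**The concern.** The same clinical event leads to two different statuses. Under 4.3.1 the subject is off drug and still followed; under 8.4.3 the subject is out of the study. Section 8.4.3 is the natural place for a site to look when combination toxicity occurs, and it does not refer to 4.3.2 or 6.4.

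If a site acts on 8.4.3 as written, tumour assessment stops and, in Phase II, survival contact stops. The efficacy definitions censor OS at the last date known alive, and PFS and TTP at the last follow-up or assessment without progression. These subjects would then be censored because of serious unresolved toxicity. Kaplan-Meier estimation assumes that censored subjects have the same later risk as those who remain. Unresolved Grade 3-4 toxicity in advanced liver cancer is a plausible reason for that to fail.

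There is a second route. The PPS, which is the main efficacy set, needs at least one post-treatment scan. A subject withdrawn before the first scan drops out of that set.

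**Working it through.** **1. The passages side by side**

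| Question | 8.4.3 | Elsewhere |
|---|---|---|
| Related Grade 3-4 event unresolved at 28 days | Both drugs stop; leaves study | 4.3.1: drug stops, with a possible exception; Phase II imaging continues |
| Is toxicity a reason to leave the study? | Yes | 4.3.2: not among the four reasons |
| Scans after stopping for toxicity | None, if out of study | 4.3.1 (Phase II), 6.4 and footnote 6: continue |
| Survival contact | None, if out of study | 6.4: every 60 days; Table 1 marks it as Phase II |
| Drug-related Grade 4 event | MGD013 stops; study ended | 8.4.1: Grade 4 rules act on MGD013; Table 5 has its own steps for brivanib and Grade 4 hyponatremia |

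The first four rows cannot all be followed together. The last row must be reconciled, because 8.4.3 does not say whose study participation ends or what happens to brivanib.

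**2. How many subjects**

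Part 1 plans 30 and 40 evaluable subjects per treatment cohort. With 10% dropout: 30/0.9 = 33.3, rounded up to 34; 40/0.9 = 44.4, rounded up to 45; 34 + 45 = 79 per cohort and 2 × 79 = 158. This reproduces the plan's 158. The documents give no rate for withdrawal under 8.4.3. Taking 5% to 20% as an assumption, 79 × 0.05 = 4 to 79 × 0.20 = 16 combination subjects would be affected.

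**3. Possible size for survival (illustration; every input is assumed)**

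Suppose a fraction w is withdrawn alive at 3 months and has true 6-month survival of 50%. The rest have 75% with constant hazard, so their 3-month survival is √0.75 = 0.866.

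- Truth: (1 − w) × 0.75 + w × 0.50
- Kaplan-Meier with the withdrawn censored: [(1 − w) × 0.866 + w] × 0.866

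| w | Truth | Kaplan-Meier | Difference (points) |
|---|---|---|---|
| 5% | 73.75% | 0.873 × 0.866 = 75.6% | 1.8 |
| 10% | 72.5% | 0.879 × 0.866 = 76.2% | 3.7 |
| 20% | 70.0% | 0.893 × 0.866 = 77.3% | 7.3 |

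Check: if the withdrawn had the same survival from month 3 to month 6 as the rest (86.6%), truth at w = 10% would be 0.9 × 0.75 + 0.1 × 0.866 = 76.2%, which equals the Kaplan-Meier figure. There is then no bias. Both its size and its direction rest on the assumed prognosis.

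For scale, the 95% half-width at 75% with 70 subjects is 1.96 × √(0.75 × 0.25/70) = 10 points.

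**4. Possible size for ORR in the PPS (illustration)**

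The first scan is at 8 weeks (56 days, ±7). Withdrawal comes 28 days after onset, so an event starting before about day 28 (21 to 35 across the window) could lead to withdrawal before any scan. The end-of-treatment visit in 6.2 lists no scan. With 6 responders among 30 treated, ORR is 20.0%. If 2, 4 or 6 non-responders leave the denominator, it becomes 6/28 = 21.4%, 6/26 = 23.1% or 6/24 = 25.0%.

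**The case against.** The strongest reply is that 8.4.3 is loose wording and nothing would be lost. Footnote 6 uses almost the same phrase, leaving the study because of toxicity, and then continues scans during survival follow-up. The summary of changes lists 4.3.1 and 4.3.2 among the sections clarified in Amendment 1 and does not mention 8.4.3, which suggests that 8.4.3 was simply not brought into line. This stands as evidence of intent. It does not remove the conflict: 8.4.3 still gives a plain instruction that the other sections contradict.

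A reader might also infer that 8.4.3 ends safety follow-up. The documents do not support that. Section 8.3.2 follows unrecovered events to resolution or stability, 6.2 follows serious events and events of special interest, 8.3.8 pursues related serious events even after consent is withdrawn, and 8.3.7 covers later drug-related deaths. What remains is narrower. The 30-day visit in 6.3 is put in doubt, and 8.3.2 lets follow-up after the last study visit go unrecorded in the eCRF, so an earlier last visit could leave an outcome out of the database.

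A reader might infer that the rule distorts the choice between monotherapy and combination for Part 2, because the 28-day sentence applies to combination only. This is not shown. Section 3.1.4 bases that choice on at least 6 responders of 30, then on the totality of safety and efficacy data, and not on Kaplan-Meier survival. The Grade 4 sentence sits in a general MGD013 paragraph and is not confined to combination subjects.

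It is also fair that OS, PFS and TTP are secondary, that Table 1 limits survival follow-up to Phase II, and that the illustrated bias is smaller than the sampling error of one cohort.

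**Conclusion.** The contradiction is real and can be read directly from the text: 8.4.3 makes unresolved combination toxicity a reason to leave the study, while 4.3.1, 4.3.2, 6.4 and footnote 6 make it a reason to stop treatment with follow-up continuing. The weight of the other sections suggests that treatment is what was meant.

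The statistical consequence is conditional. It arises only where a site follows 8.4.3 literally, and it would then be informative censoring of PFS, TTP and OS in Phase II, plus possible loss from the PPS before the first scan. It would be too strong to say that survival will be biased upward. The documents give neither the number of such withdrawals nor the later prognosis of those subjects. The 2 to 7 points for survival and the rise from 20.0% to as much as 25.0% for ORR show what assumed inputs produce; they are not estimates for this trial.

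The pregnancy wording in 8.3.10 has the same inconsistency with 4.3.1 and 4.3.2, but it should not be equated with the toxicity clause. That section already requires follow-up to the end of pregnancy, and whether imaging continues is a clinical matter.

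The point should be corrected, since survival and tumour data not collected after a withdrawal may not be recoverable.

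**What to change.** Reconcile 8.4.3 with 4.3.1, 4.3.2, 6.4 and Table 1 footnote 6 by stating three things:

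- stopping treatment for toxicity is not withdrawal from the study;
- the safety, tumour and (Phase II) survival follow-up already planned in 4.3.1, 6.3 and 6.4 continues;
- 4.3.2 is the only list of reasons for leaving the study.

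Two related passages need the sponsor's decision and not a simple substitution. The Grade 4 sentence in 8.4.3 must be reconciled with 8.4.1 and Table 5; replacing it with a general statement that study treatment ends could be read as stopping brivanib as well. The 8.3.10 wording must be reconciled with 4.3.1 and 4.3.2 without prescribing imaging. The exception in 4.3.1 with the medical monitor's permission, which 8.4.3 lacks, should be settled at the same time. No view is taken here on which drug should stop, or when.

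It would also help to state in 8.3.2 that outcomes of events unresolved when treatment stops are entered in the eCRF.

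The cost is an amendment to wording, plus some data entry if the eCRF suggestion is taken up. The visits, scans and survival contacts are already in the plan.
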